Early identification of Malignant Brain edema in laRge Artery oCclusive
stroke after Endovascular therapy (EMBRACE study)

Protocol Version Number and Date: 1.0, March 20, 2024

Background

Stroke is a significant global cause of death and disability. Endovascular thrombectomy (EVT) is currently the best treatment for acute large vessel occlusion stroke (ALVOS), as it can greatly reduce mortality and improve patient outcomes. However, only half of patients who undergo EVT achieve functional independence, and malignant brain edema (MBE), a severe complication, can occur after the procedure, leading to a poor prognosis. Previous studies have confirmed the effectiveness of early decompressive hemicraniectomy in reducing morbidity and mortality in patients with malignant brain edema. Therefore, identifying high-risk patients for MBE can help clinicians make appropriate triage and early intervention decisions, potentially saving patients' lives.

Predictive factors for post-ischemic stroke brain edema have been widely discussed, and reliable early predictive indicators have been identified, such as age, early consciousness disorders, baseline National Institutes of Health Stroke Scale (NIHSS), atrial fibrillation, hypertension, baseline blood glucose, and the level of reperfusion after EVT. Radiological factors, such as the Alberta Stroke Program Early CT Score (ASPECTS), collateral circulation rating of arteries, venous outflow status, CT perfusion core infarct volume, perfusion-based collateral status, and clot burden, are closely associated with the occurrence of MBE post-EVT. However, due to individual differences and multiple factors affecting MBE, a single factor cannot effectively predict MBE. Establishing a clinical risk prediction model can effectively identify high-risk populations for MBE at an early stage.

Aim

To design and validate a predictive model for MBE after EVT.

Design

Study Type: Observational [Patient Registry]

Time Perspective: Prospective

Study population

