The study is a multicenter, prospective, observational clinical registry study, commenced on April 1, 2024, and is expected to end in June 2027. Participants were ALVOS patients undergoing EVT treatment in neurology departments from multiple stroke centers. The data from Zhejiang Provincial People's Hospital compose the model training cohort, while data from other centers serve as an independent external validation cohort. The protocol of the study has been approved by the human Ethics Committee of Zhejiang Provincial People's Hospital (KY2024058). All clinical investigations will be conducted according to the principles set in the Declaration of the Helsinki.

Inclusion Criteria:

- (1) Age > 18 years old;
- (2) Onset of stroke to hospital admission < 24 hours;
- (3) Admission with a head CT scan ruling out hemorrhage;
- (4) Patients undergoing CT perfusion scan before treatment;
- (5) Confirmation of internal carotid artery (ICA) or middle cerebral artery (MCA) occlusion or tandem occlusion by Digital Subtraction Angiography (DSA) and subsequent EVT;
- (6) complete 3-months follow-up.

Exclusion Criteria:

- (1) Poor quality of preoperative CT perfusion imaging;
- (2) Posterior circulation occlusion or isolated anterior cerebral artery occlusion;
- (3) Presence of other severe diseases such as malignant tumors, severe organ failure, or other life-threatening conditions with an expected survival period of less than 90 days;
- (4) Incomplete imaging and clinical data.

Procedures

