All ALVOS patients will undergo comprehensive evaluation by neurologists at admission to the stroke center to obtain baseline data from clinical and laboratory examinations. Multimodality CT, including head non-contrast CT (NCCT), CT perfusion (CTP) and CTP-derived multiphase CT angiography (CTA), will be performed to assess whether patients are eligible for EVT. After EVT, all patients will be transferred to the neuro-intensive care unit for close perioperative and postoperative care to ensure stability of vital signs and implementation of comprehensive monitoring and management. This includes daily neurological assessments, monitoring of vital signs and oxygenation, and management of endotracheal intubation. Once the patient's vital signs stabilize or after the patient is extubated, they will be transferred to the neurology stroke care unit for further treatment. In principle, this trial does not involve the selection and intervention of therapeutic drugs. Within 24 hours post-EVT, patients will undergo repeat head NCCT to exclude hemorrhage and evaluate surgical outcomes. Antiplatelet therapy may be considered based on the patient's specific condition but should be cautiously selected in clinical practice and closely monitored to prevent bleeding complications. In case of signs of hemorrhagic transformation, physicians may adjust the antiplatelet therapy regimen at their discretion, potentially reducing the dose or delaying antiplatelet treatment. Additionally, regular in-hospital follow-up head NCCT scans will be performed on patients at day 3, to monitor disease progression and adjust treatment plans promptly.

Imaging protocol

Head NCCT is performed on a Toshiba Aquilion 320-slice CT scanner (Toshiba Medical Systems) using the following acquisition parameters: 120 kV, 128 mAs, scan coverage of 240 mm, and scan width of 5 mm. Simultaneously, 4-dimensional time-resolved whole-brain CTA and whole-brain CTP can be acquired. Lohexol (45 mL) (Medrad Stellant D SCT-212; Bayer Healthcare) is injected at a rate of 5

mL/second, followed by a 30 mL saline flush at an injection rate of 4 mL/second. All perfusion parameters are analyzed using post-processing software.

Radiological assessments

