The imaging variables collected in this study involve arterial, venous and perfusion status variables, including NCCT-ASPECTS, ischemic core volume, the penumbra volume, collateral status based on CTP and multiphase CTA, clot burden score, and venous outflow status. Imaging evaluations will be performed by imaging physicians who are blind to the clinical information.

CT perfusion assessment

Areas with relative cerebral blood flow (rCBF) <30% is defined as the ischemic core. The penumbra volume is calculated by subtracting the ischemic core volume (lesions with rCBF <30%) from the perfusion lesion volume (delay time threshold >3 seconds). The collateral index is defined as the volume of tissue with delay time (DT) >6 s divided by the volume with DT >2 s.

Clot burden score

We use a CBS for the anterior circulation to quantify the extent of ipsilateral intracranial thrombus, allotting major arteries 10 points for the presence of contrast opacification on CTA. Two points each is subtracted for the absence of contrast opacification in the complete cross-section of any part of the proximal M1 segment, distal M1 segment, or supraclinoid ICA, and 1 point each for M2 branches, A1 segment, and infraclinoid ICA. Partial filling defects suggesting stenosis or non-occlusive thrombus are rated as patent. A score of 10 indicates the absence of a visible occlusion on CTA, while a score of 0 indicates occlusion of all major intracranial anterior circulation arteries.

Venous outflow assessment

The outflow status of the sphenoparietal sinus, superficial middle cerebral veins, and intracerebral veins will be evaluated. Venous opacification will be graded per vein using a three-point scale based on baseline CT angiography:

- 0: Complete absence of cortical vein opacification
- 1: Moderate opacification (attenuation of one of the target veins on the contralateral side)
- 2: Full opacification.

Clinical assessments

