We will record the demographic data (gender, age, hypertension, diabetes, history of atrial fibrillation), site of occlusion, baseline systolic and diastolic blood pressure, prior IVT administration, baseline NIHSS score, NIHSS score at discharge, modified Rankin Score (mRS) at discharge, and TOAST stroke etiology (Trial of ORG 10172 in Acute Stroke Treatment) of each participant. Hematological laboratory results will include baseline glucose, baseline white blood cell count, baseline neutrophil count, baseline hemoglobin, and platelet count. The EVT operator will record the time from stroke onset to puncture (OTP), time from puncture to recanalization (PTR), and degree of blood flow restoration. The occluded vessel will be determined based on intraoperative angiography results, and reperfusion level will be graded using the modified Thrombolysis in Cerebral Infarction (mTICI) score, with complete reperfusion defined as mTICI 2b-3. Clinical assessments will be conducted by neurologists unaware of the clinical diagnosis.

Study groups

- training set

To determine potential predictive factors, imaging and clinical parameters will be enrolled into LASSO regression analysis, which effectively eliminated several irrelevant or multicollinearity independent variables to reduce high-dimensional data. The multivariable logistic regression analysis will be applied to determine the

variables predicting MBE, and the results will be used to create a predictive model based on the training set.

- validation set

The predictive model will be further validated in the validation set.

Outcome assessment

Primary Outcome Measures:

The occurrence of MBE: Patients developed MBE within 3 days post-EVT

Secondary Outcome Measures:

1. The follow-up mRS scores of enrolled patients at 90 days since stroke onset.
2. Evidence of parenchymal hemorrhage (PH type) on cranial imaging during hospitalization.

Sample size

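### The primary outcome, MBE within 3 days, has no operational criterion and no rater masked to the predictors, and the incomplete-data exclusion can drop early severe cases

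*Protocol*

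**What the plan says.** Under Outcome assessment, the primary outcome is the occurrence of MBE, specified in full as "Patients developed MBE within 3 days post-EVT". The only other description of MBE is in the Background: "malignant brain edema (MBE), a severe complication, can occur after the procedure, leading to a poor prognosis". That is a statement about prognosis and cannot be applied to a scan or a patient.

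Two follow-up head CTs are planned under Procedures. One, within 24 hours of EVT, is to exclude hemorrhage and judge the result of the procedure. For the other, "regular in-hospital follow-up head NCCT scans will be performed on patients at day 3, to monitor disease progression and adjust treatment plans promptly". Neither is named as the source of the MBE label.

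Two sentences concern blinding. Radiological assessments says "Imaging evaluations will be performed by imaging physicians who are blind to the clinical information". Clinical assessments says "Clinical assessments will be conducted by neurologists unaware of the clinical diagnosis".

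Exclusion criterion (4) is "Incomplete imaging and clinical data", with no limit to baseline data. Study population and Sample size assign the lead hospital's data to model building and internal validation, and the other centres' data to external validation.

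**The concern.** The predictors have explicit rules: a blood-flow threshold for the core, delay-time thresholds, a point-by-point clot burden score, three venous grades and a reperfusion cut-off. The outcome they are meant to predict has none. Predictor selection, AUC, calibration plots, the Hosmer-Lemeshow test, decision curves and the incidence behind the sample size all depend on that one label.

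Two things are at stake. First, if centres use the term differently, the difference coincides with the split between model building and external validation, so label error cannot be told apart from model error. A rater who knows the predictors or the predicted risk adds a bias in the flattering direction. Nothing in the text keeps the nomogram's output from whoever records MBE at an outside centre. Second, a patient who dies or is decompressed before day 3 has no scheduled day-3 scan and can fall under exclusion (4). Such patients are likely to be the most severe, so the exclusion would depend on the outcome.

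**Working it through.** **1. The Protocol's own figure.** Inputs from Sample size: 200 training events, a 7:3 split, 290 lead-centre events, 100–200 external events and 20% incidence.

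- Lead-centre events: 200 / 0.7 = 285.7, so 286 (stated as 290).
- Total: (290 + 100) / 0.20 = 1950. The stated figure is reproduced, using the lower end of the external range.

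The 20% has no definition attached. If the criterion in use gave a different incidence, the same 390 events would need:

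- 25%: 390 / 0.25 = 1560
- 15%: 390 / 0.15 = 2600
- 10%: 390 / 0.10 = 3900

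**2. The blinding sentences set beside the outcome.** The imaging sentence closes a paragraph that begins "The imaging variables collected in this study involve arterial, venous and perfusion status variables" and lists baseline measures. Edema, midline shift and follow-up CT are not among them. If it is read broadly, those readers are blind to clinical data but may still know the imaging predictors that they graded. The clinical sentence does not say which diagnosis the assessors are unaware of, and it mentions neither MBE nor the predictors.

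**3. Illustration of label error.** Assumptions, none from the Protocol except the 20%: true incidence p = 0.20; true AUC A = 0.80; a model perfectly calibrated to the lead centre's meaning of MBE; outside labels with sensitivity Se and specificity Sp relative to that meaning; label error independent of the score given true status.

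- Observed incidence: I = p·Se + (1 − p)(1 − Sp)
- Observed/expected: I / p
- PPV = p·Se / I; NPV = (1 − p)·Sp / (1 − I)
- Apparent AUC = 0.5 + (A − 0.5)(PPV + NPV − 1)

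For Se 0.90 and Sp 0.95: I = 0.18 + 0.04 = 0.22; O/E = 0.22 / 0.20 = 1.10; PPV = 0.18 / 0.22 = 0.818; NPV = 0.76 / 0.78 = 0.974; AUC = 0.5 + 0.3 × 0.792 = 0.738.

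| Se / Sp | Observed incidence | O/E | Apparent AUC |
|---|---|---|---|
| 0.95 / 0.98 | 20.6% | 1.03 | 0.77 |
| 0.90 / 0.95 | 22% | 1.10 | 0.74 |
| 0.80 / 0.95 | 20% | 1.00 | 0.73 |
| 0.80 / 0.90 | 24% | 1.20 | 0.68 |
| 0.70 / 1.00 | 14% | 0.70 | 0.78 |
| 1.00 / 0.90 | 28% | 1.40 | 0.71 |

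The third row shows that overall incidence can agree exactly while discrimination falls, so matching incidence between centres is no reassurance.

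**4. Against sampling error.** With 100 events and 400 non-events, the Hanley-McNeil 95% half-width at AUC 0.80 is about 0.055. The losses of 0.03 (95/98%) and 0.02 (70/100%) lie inside it. The 90/95% case loses 0.06, about equal to it, and the other three rows lose more.

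**5. Early death or decompression.** No arithmetic is possible because the Protocol gives no rate. The reasoning is textual: exclusion (4) is not limited to baseline data, no rule classifies a patient without a day-3 scan, and the outcome window ends at day 3.

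**The case against.** Several stronger readings are tempting, and the Protocol does not support them.

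- *That there is no blinded reading at all.* The imaging sentence is unrestricted in wording and could be stretched to follow-up scans. What stands is that no masked reader is assigned to MBE.
- *That each centre labels MBE knowing NIHSS and core volume.* The Protocol does not say who labels or what they know. If the blinded imaging readers did it, they would not know NIHSS. Nothing prevents unmasked labelling, but nothing prescribes it.
- *That the clinical blinding is unattainable.* This assumes that the assessors are the neurologists who evaluate patients at admission, which is not stated, and the diagnosis they are unaware of could be MBE status. The sentence is unclear; it is not shown to be impossible.
- *That the label cannot be repaired later.* The scans exist, so an imaging component can be re-read. A clinical component that was never recorded might be lost.

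On early death, it is fair to say that the window already covers events before day 3, that a scan is also planned within 24 hours, and that the Protocol never says a missing day-3 scan makes imaging incomplete. The exclusion therefore permits the loss of these patients without requiring it.

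The label-error figures are assumed. They cover only error unrelated to the score. Labels influenced by the predictors would push AUC up, and that effect is not quantified.

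An unseen SAP is a weak defence on the main point. The criterion for the primary endpoint governs what sites record, so it belongs in the Protocol.

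**Conclusion.** The point holds. The primary outcome has no operational criterion and no assigned rater masked to the predictors. Because centre and cohort role coincide, a difference in labelling would be confounded with model performance. Under the assumptions shown, moderate label error (90/95%) moves an AUC of 0.80 to about 0.74 and O/E to 1.10. Across the scenarios, AUC runs from 0.68 to 0.78 and O/E from 0.70 to 1.40. These figures show what the gap could do; they are not evidence that centres will disagree. The 1950 total reproduces and is not in dispute, but its 20% incidence has no definition behind it. The exclusion of incomplete data is a second, smaller defect: as worded, it allows selection that depends on the outcome.

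**What to change.** - State one MBE criterion, chosen by the sponsor, and apply it identically in all centres to the head CTs already scheduled within 24 hours and at day 3, together with any clinical component that the sponsor specifies.
- Have the study's existing imaging physicians read these scans de-identified, masked to baseline predictors and predicted risk. No one should read the follow-up scans of a patient whose baseline imaging they graded.
- Limit exclusion (4) to baseline data. Patients without a day-3 scan because of early death or decompression then stay in the analysis, with their outcome classified by a rule that the sponsor fixes in advance. Whether decompression counts as MBE is for the sponsor to decide. It is a treatment decision that may itself reflect the predictors.
- Keep the sentence on blinded clinical assessments, and say what the assessors are unaware of.

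The cost is wording, reading time for up to two scans per patient (2 × 1950 = 3900 reads at the planned size), image transfer between centres, and one re-read for patients already enrolled. No new scan or procedure is needed.

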In this study, predictive model will be constructed using the EVT database from Zhejiang Provincial People's Hospital as a training cohort, and prospective data from other centers will be used to validate the performance of predictive model. We will randomly select 70% of the patients from the Stroke Center EVT database at Zhejiang Provincial People's Hospital as the training cohort, while the remaining 30% will constitute the internal validation cohort. Within the training cohort, our aim will be to analyze imaging and clinical parameters when constructing the predictive model.

Given the requirement of at least 10 events per candidate variable for model establishment, a minimum of 200 MBE patients is necessary in the training cohort to ensure stable model estimation. Based on a study design with a sample ratio of 7:3 for the training and internal validation sets, at least 290 MBE patients will be required in this study at Zhejiang Provincial People's Hospital. The external validation set will require 100-200 positive samples; considering an approximate 20% incidence rate of MBE in anterior circulation EVT patients, this study will need to include at least 1950 EVT patients.

Statistical analysis

Compare baseline clinical and imaging data of EVT patients with and without MBE across the training, internal validation, and external validation sets. Continuous variables conforming to a normal distribution will be described using means and standard deviations, while those not conforming will be described using medians and quartiles. Categorical variables will be expressed as percentages.

In the training set, factors influencing MBE will be analyzed. Continuous variables will be analyzed using Student's *t*-test or Mann-Whitney U test, while categorical variables will be analyzed using chi-square test and Fisher's exact test. Collinearity among variables will be assessed using Variance Inflation Factors (VIFs), where VIF <10 and Tolerance >0.1 indicate no significant collinearity. Variables with a significance level of *P* <0.1 in univariate analysis will be incorporated into logistic regression analysis using forward stepwise selection method, and odds ratios (ORs) and 95% confidence intervals (CIs) will be calculated. Factors with *P* < 0.05 will be included as independent predictors of MBE in the model. After constructing the predictive model, it will be converted into a dynamic nomogram and deployed on a webpage, generating a dynamic nomogram URL.

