The dynamic nomogram URL will be used to externally validate EVT data from other stroke centers and will collect data. The area under the receiver operating characteristic (ROC) curve (AUC) will be used to evaluate the ability of the predictive model to identify high-risk MBE patients after EVT in the training, internal and external validation sets, and corresponding 95% CIs will be calculated. Calibration plots and the Hosmer-Lemeshow goodness-of-fit test will assess the consistency between actual MBE occurrence and predicted MBE risk probability in EVT patients. Decision curve analysis (DCA) will determine the clinical net benefit of the model at different risk threshold probabilities in the three sets.

Statistical analyses will be performed using IBM SPSS Statistics software (version

26.0; IBM Corporation, Armonk, NY, USA) and R software (version 4.3.1, R Development Core Team, Vienna, Austria).

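### The training cohort is defined two ways (all lead-hospital data, or a random 70% of it), and the 7:3 split behind the sample size keeps 87 of 290 MBE events out of model development

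*Protocol*

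**What the plan says.** All references are to the protocol.

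- 'Study population': the lead hospital's data "compose the model training cohort, while data from other centers serve as an independent external validation cohort". No internal split is mentioned.
- 'Sample size', opening sentence: the "predictive model will be constructed using the EVT database from" the lead hospital, which serves as the training cohort. For the other sites, "prospective data from other centers will be used to validate the performance of predictive model".
- 'Sample size', next sentence: "We will randomly select 70% of the patients from the Stroke Center EVT database" at that hospital to form the training cohort. The remaining 30% become an internal validation cohort.
- 'Sample size', calculation: at ten events per candidate variable, "a minimum of 200 MBE patients is necessary in the training cohort to ensure stable model estimation". The lead hospital's requirement of 290 or more MBE patients is then derived from the split: "Based on a study design with a sample ratio of 7:3 for the training and internal validation sets". With 100 to 200 external events and about 20% incidence, the total is at least 1,950.
- 'Study groups': one training set and one validation set. "The predictive model will be further validated in the validation set".
- 'Statistical analysis': AUC and decision curves are evaluated in training, internal validation and external validation sets, the latter "at different risk threshold probabilities in the three sets".

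The protocol mentions no bootstrap or cross-validation.

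**The concern.** There are two linked problems.

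The first is definition. 'Study population' and the opening of 'Sample size' put every lead-hospital patient in the training cohort. The following sentence puts in a random 70%. 'Study groups' knows two sets and 'Statistical analysis' three. Two analysts could therefore fit the model on different patients.

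The second is efficiency. Predictors are chosen from the data, by LASSO in 'Study groups' and by univariate screening at P<0.1 followed by forward stepwise selection in 'Statistical analysis'. Such selection becomes less stable as events fall. The split runs it at the plan's own floor of 200 events while 43% more events are in hand. In return it gives an internal check that depends on one random draw from the same hospital, alongside an external validation that is planned anyway.

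A minor point of wording: 'Sample size' contrasts the lead hospital's EVT database with prospective data from other centres. This leaves it unclear whether that database also starts prospectively on 1 April 2024.

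**Working it through.** **Inputs from 'Sample size':** 200 training events, 10 events per candidate variable, 7:3 split, 290 lead-hospital events, 100 to 200 external events, 20% incidence, 1,950 patients. The AUC values and the simulation settings below are assumptions, because the protocol gives none.

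**1. The plan's own figures.**
- Lead-hospital events: 200 / 0.7 = 285.7, stated as 290.
- Patients: 290 / 0.20 = 1,450, plus 100 / 0.20 = 500, gives 1,950. This matches, using the lower end of the external range.
- Implied candidate variables: 200 / 10 = 20.

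**2. What the split does.**
- Training: 0.7 × 290 = 203 events in 0.7 × 1,450 = 1,015 patients.
- Held out: 0.3 × 290 = 87 events in 435 patients.
- Events per variable: 203 / 20 = 10.15, against 290 / 20 = 14.5 with all the data. The ratio is 290 / 203 = 1.43.
- Coefficient standard errors are about √(290/203) = 1.20 times as large under the split.

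**3. Variation from the draw.** With an unstratified draw of 1,015 from 1,450 patients containing 290 events, the number of training events is hypergeometric.
- Mean 203; SD = √(1,015 × 0.2 × 0.8 × 435/1,449) = 7.0; 5th percentile 191 (191 / 20 = 9.6 per variable).
- P(fewer than 200) = 31%; P(fewer than 190) = 2.7%. A shortfall is fairly likely but small.

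**4. Precision of the hold-out AUC.** The Hanley-McNeil variance is [A(1−A) + (n₁−1)(B−A²) + (n₀−1)(C−A²)] / (n₁n₀), with B = A/(2−A), C = 2A²/(1+A), n₁ events and n₀ = 4n₁ non-events. At A = 0.80, n₁ = 87 and n₀ = 348 it is (0.16 + 2.293 + 24.676) / 30,276 = 0.000896. The SE is 0.0299 and the 95% half-width 0.059.

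| Assumed AUC | 87 held-out events | 100 external events |
|---|---|---|
| 0.75 | ±0.063 | ±0.059 |
| 0.80 | ±0.059 | ±0.055 |
| 0.85 | ±0.053 | ±0.049 |

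The hold-out is less precise than even the smallest planned external set, and unlike that set it cannot test other hospitals.

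**5. Like-for-like simulation.** Assumptions: 20 candidates, 8 true predictors, AUC 0.80, 20% MBE, univariate P<0.1 then forward P<0.05, and 204 replicates in two runs (77 with 60 bootstrap resamples, 127 with 50), with selection repeated in every resample.

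| | 7:3 split | All 1,450 with bootstrap |
|---|---|---|
| RMSE of internal AUC estimate against the model's true AUC | 0.024 | 0.016 |
| Mean true AUC in new patients | 0.790 | 0.794 |
| Mean calibration slope in new patients | 0.92 | 0.94 |
| Models with slope below 0.9 | 94/204 = 46% | 60/204 = 29% |

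A separate simulation with a similar selection procedure gave RMSE 0.032 against 0.016 and slopes of 0.92 against 0.94.

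**The case against.** The best defence reads the text in order: it first names the site that supplies development data, then says how those data are divided. The 7:3 ratio, the 290 and the three-set analyses all follow the split, so most analysts would follow it too. That softens the contradiction, but the term training cohort still has two memberships in adjacent sentences, and 'Study population' and 'Study groups' never mention the split.

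On efficiency, it is fair that 290 exists only because 200 was inflated by 1/0.7 to pay for the hold-out, that 203 meets the plan's target on average, and that a random hold-out is a recognised form of internal validation. The 31% chance of falling below 200 also assumes that accrual stops at exactly 290, whereas the protocol says at least 290. Discrimination barely changes (0.790 against 0.794), and the simulation leaves out the LASSO step. All of this stands, and it limits the size of the point. It does not show any advantage in withholding the 87 events once other centres provide an external set.

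The 20 candidates are back-calculated. 'Radiological assessments' and 'Clinical assessments' list about 26 variables or scores available before discharge. If all were candidates, events per variable would be 290 / 26 ≈ 11 with all the data and 203 / 26 ≈ 8 under the split. The figure of 14.5 therefore depends on the count, but the comparison still favours using all the data.

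The prospectivity point is largely answered by the protocol's general description of the study as prospective. A clarifying phrase is enough.

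**Conclusion.** The concern holds on both counts and should be fixed. The definitions conflict over which patients the model is fitted on: 1,450 with 290 events, or 1,015 with 203. There is no arithmetic error; the plan's 290 and 1,950 reproduce.

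The split is an inefficient choice. It gives up 30% of the lead-hospital events for an internal AUC known only to ±0.053 to ±0.063 (assumed AUC 0.85 to 0.75). The benefit of the alternative is real but modest: about one third less error in the internal AUC estimate (0.024 to 0.016) and slightly better calibration (slope 0.92 to 0.94). These last figures rest on the simulation assumptions: 20 candidates, 8 true predictors, AUC 0.80, 20% MBE and no LASSO step.

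**What to change.** 1. Use one definition of the training cohort in 'Study population', 'Study groups', 'Sample size' and 'Statistical analysis'. Preferably it is all lead-hospital patients, with the other centres kept as the external validation set.
2. Replace the 7:3 split with bootstrap internal validation, for example 500 to 1,000 resamples, each repeating the whole variable selection. Report optimism-corrected AUC and calibration slope.
3. Rewrite the sample-size rationale, since 290 can no longer rest on the 7:3 ratio. Ten events per variable alone would give 200 events, that is 200 / 0.20 = 1,000 lead-hospital patients and 1,000 + 500 = 1,500 in total. Keep 1,450 + 500 = 1,950 and justify 290 events as about 14.5 per variable, stating the number of candidate variables explicitly.
4. If the split is kept, stratify it by MBE and describe it in 'Study population' and 'Study groups'.
5. State whether the lead hospital's EVT database is prospective from 1 April 2024.

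The cost is protocol wording, bootstrap code and a new sample-size paragraph, with no extra patients. The one loss is the separate internal-validation column in the results.

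### The 200-event minimum meets the protocol's own rule of 10 events per candidate only for 20 or fewer candidates, a number it never states; about 26 eligible variables are listed without a cap

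*Protocol*

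**What the plan says.** The Sample size section gives both the rule and the number: "at least 10 events per candidate variable for model establishment, a minimum of 200 MBE patients is necessary in the training cohort". It presents the 200 events as what makes the model estimates stable. From there it goes to at least 290 MBE patients at the lead hospital (7:3 split) and at least 1950 EVT patients overall (20% incidence, 100-200 external events).

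The possible predictors are described elsewhere in the protocol:

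- Radiological assessments lists "NCCT-ASPECTS, ischemic core volume, the penumbra volume, collateral status based on CTP and multiphase CTA, clot burden score, and venous outflow status".
- Clinical assessments lists demographics and history, occlusion site, blood pressures, prior IVT, baseline NIHSS, TOAST class, and NIHSS and mRS at discharge. It adds: "Hematological laboratory results will include baseline glucose, baseline white blood cell count, baseline neutrophil count, baseline hemoglobin, and platelet count". The operator also records "time from stroke onset to puncture (OTP), time from puncture to recanalization (PTR), and degree of blood flow restoration".

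On what enters the model, Study groups says "imaging and clinical parameters will be enrolled into LASSO regression analysis", and Sample size says "our aim will be to analyze imaging and clinical parameters when constructing the predictive model". Statistical analysis describes a univariate screen at P<0.1, then forward stepwise logistic regression. None of these places gives a number of candidates, a list or an upper limit.

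**The concern.** A rule expressed per candidate variable can be checked only if the number of candidates is known. Here it has to be inferred as 20, and the variables that the protocol describes as imaging and clinical outnumber that. On the natural reading, in which the listed parameters are what enters selection, the planned events do not deliver the ratio from which they were derived.

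The model is to be turned into a nomogram on a public web page, so the claim of stable estimation should be one that the design supports. The number of candidates also needs to be settled before outcome data are examined. Settled later, the outcome could shape the list, and the rule would no longer mean what it says.

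**Working it through.** **Inputs.** From Sample size: 10 events per candidate, 200 training events, 7:3 split, 290 MBE patients at the lead hospital, 100-200 external events, 20% incidence, 1950 in total. The variable counts are mine, taken from Radiological assessments and Clinical assessments.

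**1. The plan's own chain.**
- Implied candidates: 200 / 10 = 20.
- MBE patients at the lead hospital: 200 / 0.7 = 285.7, stated as 290.
- Total: (290 + 100) / 0.20 = 1950, using the lower end of the external range.

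The chain is consistent, provided there are 20 candidates.

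**2. Count of listed variables.**

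| Group | Variables | Number |
|---|---|---|
| Imaging | ASPECTS, core, penumbra, CTP collaterals, multiphase CTA collaterals, clot burden, venous outflow | 7 |
| Demographic and history | sex, age, hypertension, diabetes, atrial fibrillation | 5 |
| Clinical | occlusion site, systolic and diastolic pressure, prior IVT, baseline NIHSS, TOAST | 6 |
| Laboratory | glucose, white cells, neutrophils, hemoglobin, platelets | 5 |
| Procedural | onset to puncture, puncture to recanalization, reperfusion grade | 3 |

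7 + 5 + 6 + 5 + 3 = 26. Adding discharge NIHSS and discharge mRS gives 28. I leave those two out because they are measured too late to predict MBE within 3 days of EVT.

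**3. Events per candidate = training events / candidates.**

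| Counting choice | Candidates | 200 events |
|---|---|---|
| All recorded, or the 26 with three veins entered separately | 28 | 7.14 |
| As tabulated | 26 | 7.69 |
| Two collateral measures merged | 25 | 8.00 |
| One of each overlapping pair removed (collaterals, white cells/neutrophils, the two pressures) | 23 | 8.70 |
| The same, without TOAST | 22 | 9.09 |
| Largest number that meets the rule | 20 | 10.00 |

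The planned 290 gives 290 x 0.7 = 203 training events, and 203 / 26 = 7.81, so rounding up to 290 changes little. Occlusion site and TOAST count once each here; entered as multi-level factors they would lower the ratio further.

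**4. Does any list in the protocol produce 200?** Background names predictors including "hypertension, baseline blood glucose, and the level of reperfusion after EVT" and "collateral circulation rating of arteries, venous outflow status, CT perfusion core infarct volume, perfusion-based collateral status, and clot burden". Twelve of the predictors named there are among the 26: age, baseline NIHSS, atrial fibrillation, hypertension, glucose, reperfusion, ASPECTS, arterial collaterals, venous outflow, core volume, perfusion-based collaterals and clot burden. These would need 12 x 10 = 120 events; all 26 would need 26 x 10 = 260. Neither gives 200.

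**5. Does selection restore the ratio?** No. LASSO, the P<0.1 screen and stepwise selection all use the outcome, and the rule counts candidates before that step. The collinearity check by VIF does not use the outcome. But removing one of each of the three obvious overlaps still leaves 23.

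**6. Scale of full compliance at 26.** 260 training events; 260 / 0.7 = 371.4, so 372 MBE patients at the lead hospital; (372 + 100) / 0.20 = 2360 patients in total.

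**The case against.** The best reply is that no contradiction is proved. The protocol says what is recorded and never calls that list the candidate set. The rule and the 200 events together can be read as a cap of 20. A compliant reading exists: drop white cells, neutrophils, hemoglobin, platelets and the two time intervals, and 26 - 6 = 20. Some pre-selection must be intended, since the discharge scores are recorded beside the baseline variables. The list may stand in an analysis plan that is not at hand. All totals are minimums, LASSO is a penalized method, and internal and external validation with calibration would expose overfitting.

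Much of this stands. It makes 7.7 a conditional figure, and the absence of a detailed list from the protocol is not itself the fault. It does not remove the point. The sample-size argument is made in the protocol, and its number does not follow from its rule together with the variables shown there. The six variables in the compliant reading sit under the clinical assessments with nothing setting them aside. Study groups describes LASSO as the step that thins the variables out, which fits a broad starting set better than a pre-selected 20. Later validation can reveal a poor model, but it does not make the stated ratio true.

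Two stronger readings are tempting. A reader might infer that the sample size is simply wrong and that 2360 patients are needed. The documents do not support this, because nothing commits the investigators to all 26 candidates. A reader might also infer that the model will be unstable. The arithmetic shows only that the protocol's own rule of thumb may be missed, not that estimates would be materially unstable.

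**Conclusion.** The point holds as a conditional mismatch between the sample-size rule and the variable list. The 200 events satisfy the rule at 20 or fewer candidates. At 26 they give about 7.7 per candidate, and at every count considered from 28 down to 22 they give 7.1 to 9.1, always below 10. This assumes that the listed variables are the candidates, that each counts as one, and that training events come in near the planned 200 to 203. If a list of at most 20 already exists, stating its length in the protocol closes the gap. The rest of the chain, 200 to 290 to 1950, is sound. This should be corrected, but it is no ground for enlarging the study.

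**What to change.** Reconcile the Sample size section with the variable list in one of two ways.

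1. State the number of candidates and pre-specify at most 20. Choose them without looking at outcome data, and limit them to variables known by the end of EVT, which excludes discharge NIHSS and discharge mRS. Which variables to drop is for the investigators. Removing overlapping measures is one route but not obligatory: Background treats arterial and perfusion-based collaterals as separate predictors, so there may be reason to keep both.
2. Keep the full list, restate the ratio as about 7.7 events per candidate (for 26), and soften both the requirement of at least 10 and the claim of stable estimation to match.

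The cost is protocol wording only, with no extra patients and no change to the 7:3 split or the validation cohorts. The downside is a shorter candidate list under the first option, or a less favorable stated ratio and a weaker claim under the second.
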